14.3.1 Local Patient and Stakeholder Councils

The LPSCs are comprised of 7 persons drawn from the constituencies described in **Table 11**.

Table 11. Composition of Local Patient and Stakeholder Committees

LPSC Role	Description
Chair	Facilitate the group and provide linkages with the investigative team (e.g. engagement professional) and NPSC. The facilitator should have expertise in engaging patients and other stakeholders in research. This is essential to promote timely communication, interaction and connections among scientists and the local stakeholders. The Chair should be able to translate between research language and lay language for effective communication between investigative team and LPSC.
Trial key personnel	Dementia Care Specialist providing Health System-based Dementia Care (HSDC intervention Social Worker or Case/Care Manager Consultant providing Community-based Dementia Care (CBDC)
Patient and Caregiver stakeholders	Patient/caregiver stakeholders (personal experience with dementia): consider diversity of representation for dementia stages, male/female, and communication preferences (computer/email vs. phone/mail).
Community stakeholders	Volunteers or representatives from sites where the community-based interventions will be in place such as local community centers, adult day cares, respite programs, churches or senior centers that provide resources for dementia care
Area Agency on Aging	The local Area Agency on Aging or other agency that provides applicable resources

A PRAGMATIC TRIAL OF THE EFFECTIVENESS AND COST-EFFECTIVENESS OF DEMENTIA CARE/COMPARATIVE EFFECTIVENESS OF HEALTH SYSTEM-BASED VERSUS COMMUNITY-BASED DEMENTIA CARE

Alzheimer's Association	The Alzheimer's Association or equivalent
Primary health provider stakeholder	Primary Care Physician who has patients including those with dementia
Other health provider stakeholder	A home health agency who has experience receiving referrals for patients with dementia

14.3.2 National Patient and Stakeholder Council

The NPSC is comprised of 6 persons, 2 Co-chairs and a representative from each LPSC. The NPSC: 1) serves in a consultative capacity to local councils and site PIs, various work group committees and study leadership; 2) integrates the input from the 4 local councils and communicates that to the trial's PI and committees; and; 3) coordinates activities initially for a) formulating the final research questions; b) finalizing study design; c) monitors study progress, and suggests changes and edits of all participant-facing print materials and d) provides recommendations for disseminating the results.

14.3.3 Training patients, stakeholders, and investigators

During Year 1, investigators, patients and stakeholders will undergo training, focusing on communicating what it means to be partners in patient-centered research. The training emphasized an authentic communication paradigm that builds and maintains trust, respect, and mutual understanding.

14.3.4 Engaging patients and other stakeholders as partners in all phases of the research

The bidirectional process of engaging patients and other stakeholders will take place in local councils and the NPSC throughout the duration of the project. The local councils will meet 4 times a year during years 1-4 and twice during year 5. The NPSC will continue to meet monthly throughout the duration of the study.

After year 1, the local councils will focus on refining their trial sites' local resources that support screening and recruitment strategies, the intervention(s), assessment and outcomes, and strategies for disseminating the trial's findings. These local councils will provide recommendations to the NPSC and to site PIs and continually support the local Dementia Care Specialists and Care Consultants. The NPSC will collate the information from all local councils and provide guidance to the PI and various committees.

14.3.5 Monitoring the study's progress

During recruitment, the Operations Committee will review the accrual of participants weekly and after recruitment, the collection of outcomes at its weekly meeting. The SAC and DSMB will also review the study's progress. In addition, each committee will review progress of its responsibilities at the monthly meetings.

14.3.6 Dissemination and implementation of study findings

The project team will prepare a summary of findings that will be sent by mail to all study participants, including their caregivers. This summary will be reviewed and vetted by the National and Local Patient/Family Stakeholder Committees to ensure that the reading level, formatting, and content of the material are appropriate for the target group of participants. The project team has had experience providing updates of findings about improved dementia care through the UCLA ADC newsletters. This summary of findings will be

A PRAGMATIC TRIAL OF THE EFFECTIVENESS AND COST-EFFECTIVENESS OF DEMENTIA CARE/COMPARATIVE EFFECTIVENESS OF HEALTH SYSTEM-BASED VERSUS COMMUNITY-BASED DEMENTIA CARE

translated into Spanish and, if appropriate, adapted to suit the population of a specific region. In addition to an individual mailing to each participant/caregiver, this information will be conveyed through the project's website.

A Publications Committee will be established to oversee the dissemination of the study findings. It will include members of the NPSC and investigators with content expertise. This structure will allow the stakeholders and investigators to jointly address 1) how to disseminate the study findings to impact clinicians, patients, policy makers, communities, CMS and other payers; and 2) how study interventions can be scaled up for wider implementation. Also, LPSCs will work with site investigators to plan dissemination in their local communities. The patients and stakeholders can be effective particularly in influencing the policies of CMS and other payers, which can facilitate the adoption of the intervention. In addition to publications in scientific journals, the Publications Committee will plan presentations at scientific meetings, and orchestrate presentations to stakeholders, the media, payers, and policymakers.

If HSDC proves to be superior, dissemination will be less of an issue for systems that serve high percentages of capitated patients (i.e. Medicare Advantage), since the program would achieve cost savings if it is as effective as the original UCLA demonstration (\$2100 per year cost savings, CMS unpublished data). However, an initial upfront investment will be required. Work on disseminating HSDC, funded by the Commonwealth Fund, will create business cases for adopting organizations to determine how soon they will be able to recapture their investment. In addition, some healthcare systems that have strong cultures of team care may want to adapt the intervention by using BSN registered nurses as Dementia Care Specialists, thereby reducing staffing costs and addressing access in areas that may lack advance practice nurses. If major departures occur (e.g., substituting a BSN registered nurse for a nurse practitioner DCS), then the model would need to be evaluated for fidelity to ensure that similar care is provided. In fee-for-service environments, under the current reimbursement structure, HSBC would likely not generate revenue after costs of the intervention are considered. Nevertheless, there are new and emerging cost reimbursement mechanisms (e.g. 99483 cognitive assessment code, Chronic Care Management) that can be used to offset significant costs. Other obstacles to disseminating HSDC include the lack of a trained workforce and the availability of nurse practitioners who can fill the Dementia Care Specialist role. A grant under consideration by the John A. Hartford foundation for their December 2018 Board meeting would fund the development of a hands-on, in-person skill-building sessions to train nurse practitioners to become Dementia Care Specialists.

If CBDC proves to be superior, health systems that serve high percentages of capitated patients may opt to contract with community-based organizations to provide this service as a member benefit. Systems that largely care for fee-for-service patients will likely have financial obstacles to implement this program. Nevertheless, if CBDC confers clinical advantages, other mechanisms through the Agency for Community Living (ACL) or new Medicare mechanisms might be created to support this program.

If either HSDC or CBDC is superior, diffusion will need to be planned and an organization will need to assume responsibility for ensuring the fidelity within adopting health systems. Such an organization will need to be identified or created.

A PRAGMATIC TRIAL OF THE EFFECTIVENESS AND COST-EFFECTIVENESS OF DEMENTIA CARE/COMPARATIVE EFFECTIVENESS OF HEALTH SYSTEM-BASED VERSUS COMMUNITY-BASED DEMENTIA CARE

**REFERENCES****APPENDIX A: Determination of Cutpoints for HTE Subgroups****APPENDIX B: DSMB Tables, Listing and Figures**

## 1. STUDY SYNOPSIS

Title	COMPARATIVE EFFECTIVENESS OF HEALTH SYSTEM-BASED VERSUS COMMUNITY-BASED DEMENTIA CARE/ A PRAGMATIC TRIAL OF THE EFFECTIVENESS AND COST-EFFECTIVENESS OF DEMENTIA CARE
Study Design	The design is a pragmatic randomized 3-arm superiority trial. The unit of randomization is the patient/caregiver dyad.
Study Duration	6 years
Trial Sites	4 trial sites: Baylor, Scott, & White Health; Geisinger Health; University of Texas Medical Branch Health Care System; Wake Forest University
Objective	Conduct a pragmatic randomized trial to determine the comparative effectiveness and cost-effectiveness of two evidence-based models of comprehensive dementia care as well as the effectiveness and cost-effectiveness of both arms versus enhanced usual care.
Number of Subjects (Target)	2150: 1000 in each intervention arm and 150 in the usual care group
Main Inclusion Criteria	Community-living, including Assisted Living Facilities (cannot reside in a nursing home at the time of recruitment), persons with diagnosis of dementia established by a physician or other primary care provider (PCP), have family or friend caregiver(s) who speak English or Spanish, and have a PCP who is willing to partner with the program
Interventions	
Health systems-based dementia care (based on the UCLA Alzheimer's and Dementia Care program) provided by a nurse practitioner or physician's assistant Dementia Care Specialist who works within the health system.
 
Community-based dementia care (using the BRI Benjamin Rose Institute Care Consultation model) provided by a social worker or nurse Care Consultant who works at a community-based organization (CBO).
 
Both arms include structured assessments and creation of care or action plans, care coordination, and caregiver education and support, but they differ in key areas including the frequency and mode of communication with persons with dementia and caregivers, the degree of integration into the health system, including order-writing capability and use of the electronic health record.
 
Usual care with consistent referral to Alzheimer's Association Helpline ([name]) to speak to master's level consultants for decision-making support, crisis assistance, caregiver education, and referral to local programs and services.

Duration of Intervention and Follow-up	18 months
Primary Outcome	Behavioral symptoms and resulting caregiver distress as measured by the NPI-Q Severity and Modified Caregiver Strain Index scales.

Primary Analysis	All analyses will be according to intent to treat. The analysis of the two primary outcomes – NPI-Q Severity and Modified Caregiver Strain Index scores – will be done using a longitudinal repeated measures analysis based on maximum likelihood methods adjusted for the stratified randomization by site. Treatment differences will be summarized by least square means and multiplicity corrected confidence intervals.
Secondary Outcomes	NPI-Q Distress, caregiver unmet needs and confidence, and caregiver depressive symptoms.
Tertiary Outcomes	Patient long-term nursing home placement, functional status, cognition, goal attainment scaling (GAS), “days spent at home”, Dementia Burden Scale-Caregiver, a composite measure of clinical benefit, Quality of Life of persons with dementia, Positive Aspects of Caregiving
Cost-effectiveness Analysis	Ratio of incremental net Medicare costs to incremental effects of the two primary outcomes, costs to Medicaid and consumers, changes in utilization by type of use, caregiver costs for spouses who have fee-for-service Medicare
Interim Analysis	Because this is a minimal risk trial with a relatively short follow-up period (18 months), no monitoring for efficacy or futility is proposed; only monitoring for safety will be done.

## **2. STUDY OBJECTIVES AND SPECIFIC AIMS**

D-CARE is a pragmatic randomized clinical trial of 2150 participants at four diverse clinical trial sites (CTS) to compare the effectiveness and cost-effectiveness of 18 months of health systems-based dementia care (HSDC, based on the UCLA Alzheimer's and Dementia Care program) provided by a nurse practitioner Dementia Care Specialist (DCS) who works within the health system versus community-based dementia care (CBDC, using the BRI Benjamin Rose Institute Care Consultation model) provided by a social worker or nurse Care Consultant who works at a CBO versus usual care (UC).

The study's Specific Aims are:

1. To engage 4 sets of health systems and community-based organizations, patients, families, and other stakeholders in a pragmatic clinical trial
2. To adapt and implement 2 dementia care interventions at each CTS, including training of DCS' and Care Consultants and pilot testing of the interventions, assessments, and outcomes
3. To recruit 2150 participants and randomize them to receiving HSDC (N=1000), CBDC (N=1000), or usual care (N=150)
4. To administer the interventions for 18 months for all participants
5. To collect self/caregiver-reported outcomes and use claims data to evaluate other secondary and tertiary outcomes
6. To compare the effectiveness of the 2 dementia care interventions versus each other and versus usual care
7. To conduct a cost-effectiveness analysis of the two intervention arms versus each other and versus usual care

8. To conduct analyses of tertiary outcomes of both interventions versus usual care including mortality, time spent at home, long-term nursing home placement, patient/caregiver satisfaction, goal attainment scaling (in the 2 active intervention groups) and comparing all three groups on several types of utilization and out-of-pocket expenses. We will assess physician satisfaction with dementia care provided by the 3 treatment groups.

### **3. RANDOMIZATION**

At the time of the in-person or telephone (after the start of the 2020 COVID-19 pandemic) baseline assessment, caregiver and, if the person with dementia is capable, patient informed consent will be obtained. Upon successful completion of baseline measures, eligible persons will then be randomized to either HSDC or CBDC or UC in a 7:7:1 ratio. The randomization will be stratified by site using a permuted block design with a fixed block size of 15; using variable block sizes is not practical given the size of the block and the few numbers of participants to be enrolled in the usual care arm at each site. The randomization scheme will be computer-generated, and the allocation sequence will be concealed. Intervention assignment will be delivered by a web-based clinical trial management system. Because all the care processes employed in all arms reflect standard of care, the consent will focus only on the collection of data. This approach is the same as that employed in the PCORI- and NIA-funded Strategies to Reduce Injuries and Develop confidence in Elders (STRIDE) pragmatic multisite trial aimed at reducing serious falls-related injuries.

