A PRAGMATIC TRIAL OF THE EFFECTIVENESS AND COST-EFFECTIVENESS OF DEMENTIA CARE/COMPARATIVE EFFECTIVENESS OF HEALTH SYSTEM-BASED VERSUS COMMUNITY-BASED DEMENTIA CARE

STUDY PROTOCOL

TITLE: **COMPARATIVE EFFECTIVENESS OF HEALTH SYSTEM-BASED VERSUS COMMUNITY-BASED DEMENTIA CARE/ A PRAGMATIC TRIAL OF THE EFFECTIVENESS AND COST-EFFECTIVENESS OF DEMENTIA CARE**

PI: **[name]**

CO-I'S AND SITE PI'S: **[name], PHD; [name]; [name]; [name]; [name], PHD; [name], PHD; [name]; [name]**

APPLICANT CONSORTIUM:

FUNDING AGENCIES: **PCORI/NIA**

PCORI GRANT NUMBER: **PCS-2017C1-6534**

NIA GRANT NUMBER: **1 R01 AG061078-01**

APPLICANT ORGANIZATION: **UCLA**

DATE OF INITIAL IRB APPROVAL: **1/15/2019**

VERSION DATE: **07/01/24**

VERSION NUMBER: **8.0**

A PRAGMATIC TRIAL OF THE EFFECTIVENESS AND COST-EFFECTIVENESS OF DEMENTIA CARE/COMPARATIVE EFFECTIVENESS OF HEALTH SYSTEM-BASED VERSUS COMMUNITY-BASED DEMENTIA CARE

Title	COMPARATIVE EFFECTIVENESS OF HEALTH SYSTEM-BASED VERSUS COMMUNITY-BASED DEMENTIA CARE/ A PRAGMATIC TRIAL OF THE EFFECTIVENESS AND COST-EFFECTIVENESS OF DEMENTIA CARE
Study Design	The design is a pragmatic randomized 3-arm superiority trial. The unit of randomization is the patient/caregiver dyad.
Study Duration	6 years
Trial Sites	4 trial sites: Baylor, Scott, & White Health; Geisinger Health; University of Texas Medical Branch Health Care System; Wake Forest University
Objective	Conduct a pragmatic randomized trial to determine the comparative effectiveness and cost-effectiveness of two evidence-based models of comprehensive dementia care as well as the effectiveness and cost-effectiveness of both arms versus usual care.
Number of Subjects (Target)	2150: 1000 in each intervention arm and 150 in the usual care group
Main Inclusion Criteria	Community-living, including Assisted Living Facilities (cannot reside in a nursing home at the time of recruitment), persons with diagnosis of dementia established by a physician or other primary care provider (PCP), have family or friend caregiver(s) who speak English or Spanish, and have a PCP who is willing to partner with the program

A PRAGMATIC TRIAL OF THE EFFECTIVENESS AND COST-EFFECTIVENESS OF DEMENTIA CARE/COMPARATIVE EFFECTIVENESS OF HEALTH SYSTEM-BASED VERSUS COMMUNITY-BASED DEMENTIA CARE

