2. STUDY OBJECTIVES

This pragmatic randomized clinical trial of 2150 participants at four diverse clinical trial sites will compare the effectiveness and cost-effectiveness of 18 months of health systems-based dementia care (based on the UCLA Alzheimer's and Dementia Care program) provided by a nurse practitioner Dementia Care Specialist who works within the health system versus community-based dementia care (using the BRI Benjamin Rose Institute Care Consultation model) provided by a social worker or nurse Care Consultant who works at a CBO and will compare both dementia care interventions to usual care. Caregivers and patients bring their unique personal perspectives of how dementia affects their lives, what outcomes are important to them, and what attributes of the interventions render them feasible, scalable, and sustainable. The clinical sites bring participants, clinical environments, and expertise in patient-centered research and implementation. The investigators, patients, and other stakeholders planned and prepared this protocol jointly; these partners will continue to be collaboratively engaged in all aspects of the trial's implementation.

The study's Specific Aims are:

1. To engage 4 sets of health systems and community-based organizations, patients, families, and other stakeholders in a pragmatic clinical trial
2. To adapt and implement 2 dementia care interventions at each CTS, including training of DCS' and Care Consultants and pilot testing of the interventions, assessments, and outcomes
3. To recruit 2150 participants and randomize them to receiving HSDC (N=1000), CBDC (N=1000), or usual care (N=150)
4. To administer the interventions for 18 months for all participants
5. To collect self/caregiver-reported outcomes and use claims data to evaluate other secondary and tertiary outcomes
6. To compare the effectiveness of the 2 dementia care interventions versus each other and versus usual care
7. To conduct a cost-effectiveness analysis of the two intervention arms versus each other and versus usual care
8. To conduct analyses of tertiary outcomes of both interventions versus usual care including mortality, time spent at home, long-term nursing home placement, patient/caregiver satisfaction, goal attainment scaling (in the 2 active intervention groups), and comparing all three groups on several types of utilization and out-of-pocket expenses. We will assess physician satisfaction with dementia care provided by the 3 treatment groups.

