7. STUDY PROCEDURES AND VISITS

7.1 Randomization

At the time of the in-person or telephone (after the start of the 2020 COVID-19 pandemic) baseline assessment, caregiver and, if the person with dementia is capable, patient informed consent will be obtained. Upon successful completion of baseline measures, eligible persons will then be randomized to either HSDC or CBDC or UC in a 7:7:1 ratio. The randomization will be stratified by site using a permuted block design with a fixed block size of 15; using variable block sizes was not practical given the size of the block and the few numbers of participants to be enrolled in the usual care arm at each site. The randomization scheme will be computer-generated and the allocation sequence concealed. Intervention assignment will be delivered by the web-based clinical trial management system. Because all of the care processes employed in all arms reflect

A PRAGMATIC TRIAL OF THE EFFECTIVENESS AND COST-EFFECTIVENESS OF DEMENTIA CARE/COMPARATIVE EFFECTIVENESS OF HEALTH SYSTEM-BASED VERSUS COMMUNITY-BASED DEMENTIA CARE

standard of care, the consent will focus only on the collection of data. This approach is the same as that employed in the PCORI- and NIA-funded Strategies to Reduce Injuries and Develop confidence in Elders (STRIDE) pragmatic multisite trial aimed at reducing serious falls-related injuries.

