Comparison	Difference to be detected	Power for MCSI	Power for NPI-Q Severity	Overall Power	Adjusted Sample Sizes
HSDC vs. CBDC	1.5	95%	95%	90%	1000 per group
HSDC or CBDC vs. UC	3.0	95%	95%	90%	1000 HSDC and CBDC vs. 150 UC

The inflation of sample size for censoring due to deaths and losses is conservative because the data will be analyzed using longitudinal methods under the MAR assumption that include all available data on each participant. Considering the first patient follow-up for the two primary outcomes is at 3 months, the effective censoring rate for analytical purposes is approximately 5% for the primary analysis (i.e., those without any primary outcome follow-up data).

Heterogeneity of treatment effects (HTE) for the two primary outcomes will be assessed in six subgroups of participants: high vs. low patient function by FAQ, high vs. low patient function by ADL, high vs. low NPI-Q Severity, high vs low MCSI at baseline, spouse caregiver vs. other caregiver, and white non-Latino vs. nonwhite or Latino. The study will have approximately 90% power to detect interactions (differences in treatment effects between subgroup categories) of about 3 units for both NPI-Q severity and MCSI for the HSDC vs. CBDC comparisons. Interactions on the order of 6 units can be detected with approximately 90% power for comparisons of HSBC and CBDC with UC for the two primary outcomes. These detectable interactions assume a conservative Bonferroni adjusted type I error of $0.05/(6 \times 3 \times 2) = 0.0014$ to control for multiplicity. (In the analysis, we will conduct one global test of interaction per subgroup for 6 subgroups). Using an anchor-based approach that compares changes in NPI-Q measures with other clinical measures, the MCID for the severity scale is 3.2.⁶ Hence, based on this range of MCID, the study will have adequate power to detect clinically meaningful differences in subgroups for comparisons between the two interventions. However, only large interactions can be detected for the comparisons with UC because of the smaller sample size in this arm. Although equal subgroup sample sizes were assumed in the calculations, power will not be greatly affected if the imbalance in subgroup sample sizes is not more extreme than a ratio of 2:1.

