## **6. SAMPLE SIZE**

### **6.1 Primary Outcomes**

The assumptions used to determine sample size for testing differences among the three treatment arms for the two primary outcomes were: 1) type I error  $0.05/6 = 0.0083$  adjusted for 3 treatment comparisons (HSDC vs. CBDC, HSDC vs. UC and CBDC vs. UC) times 2 primary outcomes, 2) standard deviation (SD) for NPI-Q severity of 6.5 units and SD for MCSI of 6.7 units, 3) treatment difference for HSDC vs. CBDC of 1.5 units, 4) treatment difference for HSDC and CBDC vs. UC = 3, and 5) lost to follow up over 18 months because of death and dropout of 25%. The detectable treatment difference of 1.5 units for HSDC vs. CBDC is based on data reported in the literature suggesting a minimally clinical important difference (MCID) ranging from 2.8 to 4.0 (Mao et al., 2015). Given that both intervention arms will be receiving an intervention, we reduced the detectable difference in half to 1.5. Data from two studies (Callahan et al., 2006; [name], 2016) indicate that the expected benefit between HSDC and UC would be 3.2 units for NPI-Q Severity score. Based on these data we used a difference of 3 units for comparisons with UC. The estimates of the standard deviations (SD) for the 18-month NPI-Q Severity score and MCSI are 6.5 and 6.7, respectively, based on UCLA pilot data. An 18-month censoring rate of 25% was assumed because of death (15%) and dropout (10%). The

death rate was taken from fee-for-service claims data on 274 UCLA patients with a mean survival time of 1.5 years.

Sample size was first determined for the comparison between HSDC and CBDC because the effect size is smaller. The goal was to achieve at least 90% overall power for testing both outcomes. Testing each outcome at 95% power with a sample size of 1000 subjects per treatment group (adjusted for censoring) gives at least 90% overall power for testing both outcomes. Given these sample sizes, the sample size is 150 (for UC adjusted for censoring) for comparisons with the two interventions giving an overall power of at least 90%. For conservatism, we assumed the same effect size for both interventions compared with UC even though we hypothesize that HSDC will be superior to CBDC. The total sample size for the trial is 2150 individuals (adjusted for censoring).

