## 6.2 Secondary and Tertiary Outcomes

For the three secondary outcomes (NPI-Q Distress, caregiver depression (PHQ-8), Caregiver self-efficacy), we determined the detectable effect sizes assuming a Bonferroni adjusted type I error of  $0.05/(3 \times 3) = 0.006$  to control for multiplicity. The detectable effect sizes with 90% power for the three continuous measures (NPI-Q Distress, caregiver depression (PHQ-8), Caregiver self-efficacy) are on the order of 0.20 for testing HSDC vs. CBDC. For testing HSDC/CBDC vs. UC, there will be approximately 90% power to detect effect sizes on the order of 0.40. Thus, we will have good power to detect small to moderate effects for the three continuous outcomes.

Power determinations for tertiary outcomes were not performed because these are considered exploratory. Sample size and power were calculated using Power and Sample Size (PASS) software (Kaysville, UT, 2013).

The goal attainment scaling (GAS) tertiary outcome will be collected only from caregivers (in the two active intervention groups) enrolled through December 15th, 2020. Goals will be set at baseline and will be assessed at two follow-up time points: at 6-12 months and 15-18 months after enrollment. After considering the expected loss to follow up, we anticipate 80% power (appropriate for a tertiary outcome) to detect a 10% difference between HSDC and CBDC arms.

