## **8. DATA COLLECTION AND DATA FREEZE**

Data collected from date of study initiation (6/18/2019) to last date of 18-month study follow-up interview (08/21/2023) will be used. The trial database for primary, secondary and safety outcomes was closed/frozen on 4/9/2024 and considered ready for final analysis. Data lock for tertiary outcomes will be done at a later date, e.g., after resolution of fidelity data and receipt of CMS data.

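### Does 7:7:1 allocation in blocks of 15 undermine the planned usual care arm of 150?

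*SAP*

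**What the plan says.** Protocol section 7.1 and SAP section 3 describe the same scheme. SAP section 3 states that "eligible persons will then be randomized to either HSDC or CBDC or UC in a 7:7:1 ratio". Protocol section 7.1 adds that randomization is stratified by site, "using a permuted block design with a fixed block size of 15". Each full block therefore holds 7 HSDC, 7 CBDC and 1 UC dyad. Both sections explain that varying the block size was impractical, because the block is already large and each site enrols few UC dyads.

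The sizes are given separately. The synopses, in a row labelled as a target, read "2150: 1000 in each intervention arm and 150 in the usual care group". The third specific aim in both documents repeats the three arm sizes without calling them targets. The power tables (Protocol Table 5, SAP Table 2) use "1000 HSDC and CBDC vs. 150 UC" for the UC comparisons, and the text before them presents 150 as the UC number after allowance for censoring.

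Neither document says that 7:7:1 only approximates 1000/1000/150.

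**The concern.** Taken literally, the ratio, the total and the arm sizes cannot all hold. The arm sizes sum exactly to 2150, and 150 is presented as a calculated requirement, not as a rounding of 143. A reader who applies the allocation rule to the total arrives at a smaller UC arm.

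UC is by far the smallest arm and enters two of the three pairwise comparisons, so its size drives the precision of both. If 150 were the minimum needed for the stated power, a rule that delivers fewer would leave those comparisons short. A later reader might also take a UC arm of about 143 as under-recruitment or an allocation fault.

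**Working it through.** **Inputs.** Ratio 7:7:1, block size 15, four sites (Protocol 7.1, SAP 3, synopses). Total 2150 and arms 1000/1000/150 (synopses, aims). Two-sided alpha 0.05/6 = 0.0083; SD 6.5 (NPI-Q Severity) and 6.7 (MCSI); difference 1.5 between interventions and 3 against UC; 25% loss (Protocol 8.3.1, SAP 6.1).

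**Power formula.** Power = Φ(Δ / (SD × √(1/n₁ + 1/n₂)) − 2.638), with n = 0.75 × arm size; 2.638 is the normal quantile for two-sided 0.05/6. A lower bound for rejecting on both outcomes is p₁ + p₂ − 1.

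**The plan's own figures first.**
- HSDC vs CBDC, 1000 per arm (750 evaluable): 96.6% NPI-Q Severity, 95.5% MCSI, both at least 92.2%. Stated: 95%, 95%, 90%.
- 1000 vs 150 UC (750 vs 112.5 evaluable), NPI-Q Severity: standard error 6.5 × √(1/112.5 + 1/750) = 0.657; 3/0.657 = 4.565; Φ(4.565 − 2.638) = 97.3%. MCSI: standard error 0.677; Φ(4.429 − 2.638) = 96.3%. Both: at least 93.6%.
- UC size needed for 95% on MCSI against 750 evaluable: 105 evaluable, and 105/0.75 = 140 enrolled.

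The stated power is reproduced. On these inputs the binding requirement for UC is 140, so 150 carries a margin.

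**What the rule gives at 2150.** 2150/15 = 143.3 UC and 2150 × 7/15 = 1003.3 in each intervention arm. The UC gap is 150 − 143.3 = 6.7, or 4.4% of 150.

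**Range with incomplete last blocks.** Write each site total as 15kᵢ + rᵢ, with rᵢ from 0 to 14. Because 2150 leaves remainder 5 on division by 15, the four rᵢ must sum to 5, 20, 35 or 50, with 143, 142, 141 or 140 full blocks.
- Minimum UC: 140 full blocks and no UC in any incomplete block, 140.
- Maximum UC: 143 full blocks and a UC in each of four incomplete blocks, 147.
- Smallest total at which 150 is possible: 146 × 15 + 4 = 2194. It is the expected number at 150 × 15 = 2250.

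**Power against UC over that range** (whole-number arms, 25% loss):

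| Active vs UC | NPI-Q Severity | MCSI | Both, at least |
|---|---|---|---|
| 1000 vs 150 | 97.3% | 96.3% | 93.6% |
| 1001 vs 147 | 97.0% | 96.0% | 93.1% |
| 1003 vs 143 | 96.7% | 95.5% | 92.2% |
| 1005 vs 140 | 96.3% | 95.2% | 91.5% |

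The noncentral t distribution gives 96.3%, 95.1% and 91.3% in the last row. At the 5% effective censoring that both documents consider realistic for the primary analysis, 1003 vs 143 gives 99.2% and 98.8%.

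**Other power statements against UC.**
- Secondary outcomes, effect size 0.40, alpha 0.006, 25% loss: Φ(0.40/√(1/112.5 + 1/750) − 2.748) = 88.7% at 1000 vs 150, and 87.0% at 1003 vs 143. At 5% loss, 1003 vs 143 gives Φ(0.40/√(1/135.85 + 1/952.85) − 2.748) = 94.7%.
- Six-unit interaction, alpha 0.05/36, equal subgroups, 25% loss: from 91.4% (NPI-Q Severity) and 89.1% (MCSI) to 89.9% and 87.3%.

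The documents give approximately 90% for each. The shifts are 1.5 to 2 points, and the secondary figure is already a little under 90% at 150.

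**The case for a change.** The case for acting is that the documents do contradict each other. The third aim states the arm sizes as what will be randomized, 150 is a calculated number, and the rule cannot yield it at exactly 2150. One sentence would settle the matter and would spare a reader from taking a UC arm of about 143 as a recruitment failure. MCSI power at 140 clears 95% only narrowly, so it is fair to want that on record.

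The mismatch stands as a fact, and so does the missing sentence. The claim that 150 cannot arise is weaker than it looks. It needs a final total of exactly 2150, one block sequence per site and blocks filled in order, whereas the synopses call the sizes targets. At 2194 dyads, 2% over target, 150 becomes possible. Matching 1000:1000:150 exactly means 20:20:3, whose smallest block is 43; in a design that already regards 15 as large, 7:7:1 is a reasonable whole-number approximation.

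The sentence would also come late. SAP section 8 records that "The trial database for primary, secondary and safety outcomes was closed/frozen on 4/9/2024", so the real arm sizes exist and will be reported. The 1000 versus 150 calculation should remain the planning record in any case, since it is what was entered when "Sample size and power were calculated using Power and Sample Size (PASS) software".

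**Conclusion.** The target sizes and the allocation ratio are not reconciled, but the gap is a rounding that nobody labelled. At exactly 2150 dyads it amounts to about 7 UC dyads (4.4%), with UC between 140 and 147 if each site has one block sequence filled in order. The standard error of a comparison with UC rises by about 2% (0.671/0.657 = 1.021 for NPI-Q Severity).

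The stated primary power of 95% per outcome and 90% overall is met throughout that range under the plan's SDs, differences, alpha and 25% loss. That assurance covers the primary outcomes only. Power for the secondary effect size of 0.40 against UC falls from 88.7% to 87.0% at 25% loss, a small move relative to a figure given as approximate.

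No estimate, test or confidence interval depends on whether the target was 143 or 150, because SAP section 9.3 analyses dyads as randomized. Enrolment, randomization and analysis stay as they are. A remark that the ratio approximates the targets would be harmless but would alter nothing.
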